2.1 Evaluation of operational characteristics (invalid and indeterminate rates) of Typhoid RDTs

Primary Endpoint:

- 1.1 Point estimates of sensitivity and specificity for each test, with 95% confidence interval, using blood culture as reference standard.\
- 1.2 Establishment of a biorepository of well characterized specimen collection at the site available for future assessments of emerging technologies

Secondary Endpoints:

2.1 Estimates of operational characteristics of different RDTs based on quantitative assessment including invalid and indeterminate rates

DESIGNS AND METHODOLOGY

Trial Site

The study will take place in three hospitals in Nairobi County, found in Sub-Saharan Africa (Kenya). The three hospitals in Nairobi are Mbagathi County Hospital, [name]; Medical Missionaries of Mary, Reuben Centre Hospital in Mukuru Slum, Embakasi and City Council Clinic in Mukuru Slum, Embakasi.

Justification for selectig the the three study hospitals: Mbagathi County Hospital, [name] draws majority of its patients from Kibera informal settlement (slum), an area with high burden of bacterial infections due to poor sanitation and limited resources. Kibera is a large, densely populated (77,000 persons/km²) urban settlement situated within Nairobi, a city with >4 million inhabitants. It is characterized by poor sanitation evidenced by excreta and garbage in footpaths and open sewers. Water supply in Kibera is largely unregulated and food vendors trade outdoors under minimal hygiene standards (Njuguna, 2013).

Medical Missionaries of Mary, Reuben Centre Hospital and City Council Clinic are located with andserves Mukuru informal settlement (slum) population. Maukuru slum also suffers from high bacterial disease burden due to poor sanitation and limited resources. Mukuru slum (20 km East of Nairobi) is home to a population of over 150,000 in an area approximately 2km²(population density, 75,000/km²) [Kenya Population Census, 2010] living in congested housing and under poor sanitary conditions. The majority of the populations work in nearby industrial areas.

Study Design

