The reported values for prevalence of Salmonella Typhi positive patients in Kenya is 5% (Data from personal communication with [name] Co-PI). The reported values of sensitivity and specificity of diagnostic tests are generally low, (Review article on typhoid RDTs summarizes TUBEX test from IDL Biotech has sensitivity of 78% and specificity of 87%, TestTM It from LifeAssay has sensitivity of 69% and specificity of 90%, Typhidot from Reszon Diagnostic has sensitivity of 78% and specificity of 77%.(9) Similarly reported sensitivity and specificity of SD Bioline Salmonella Typhi IgG/IgM from Abbot and Typhoid IgG/IgM Combo rapid test from CTK Biotech are 69%/76% and 40-79%/68-79% respectively (15)). For the purpose of determining the sample size, sensitivity and specificity were both assumed to be 50%, which corresponds to the scenario that requires the highest number of samples to estimate sensitivity and specificity. Based on this hypothesis, and on the feasibility of recruitment at the sites of enrolment, it was decided to set the sample size in order to recruit at least 100 culture positive and culture negative samples in Kenya. These sample sizes will allow to estimate the sensitivity of the test with 80% power to detect a 95% confidence interval of width of +/- 14% in Kenya (11). Based on the prevalence mentioned above, this number of positive samples requires the enrolment of at least 2,000 participants in Kenya (at a prevalence of 5%). From a similar study carried out by an MSc student in our lab that we supervised (Performance of tubex® tf IGM antibody test against culture in typhoid fever detection in Nairobi county, MSc Thesis by [name], JKUAT, 2019), the average number of patients presenting with febrile illnesses at Mbagathi County Hospital was 20 per day, using this as a basis and considering their relatively smaller sizes, we estimate that for Medical Missionaries of Mary, Reuben Centre Hospital and City Council Clinic, we will have 10 and 5 patients presenting per day in Medical Missionaries of Mary, Reuben Centre Hospital and City Council Clinic respectively. We plan to sample for only 3 days in a week (Mon-Wed) due to the observed trend of high patient inflow on these days from [name]

[name]'s MSc work (total 35 patients per day, 420 per month). This works out to a minimum of 2,520 which is above the sample size of 2,000 participants that we are targeting.

TRIAL PROCEDURES

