The statistical analysis plan (SAP) will be developed and finalized before the start of enrolment and will describe in detail the methodology used to evaluate each of the endpoints. This section is a summary of the planned statistical analyses of the primary and secondary endpoints.

Endpoint	Statistical Analysis Methods
1.1	Point estimates of sensitivity and specificity for each test with 95% confidence interval, using Blood culture as reference standard.
1.2	Establish a biorepository of well characterized specimen collection that can be used to evaluate emerging tests.
2.2	Evaluation of operational characteristics of different RDTs including invalid and indeterminate rates.

- Efficacy Analyses

Analysis datasets

The following datasets will be defined:

- ITT (Intention-To-Test) all subjects successfully enrolled in the study
- MITT (Modified-Intention-To-Test) all subjects in ITT for whom at least one test result is available
- PP (Per-Protocol) all subjects in ITT for whom results for all tests are available (complying with the protocol)

Description of statistical methods

General approach

Estimates of accuracy

Table 5 summarizes the way results of diagnostic tests are reported when two tests are compared. Based on the definitions in the table, the following values are defined:

Sensitivity = TP / (TP + FN)

Specificity = TN / (FP + TN)

For each point estimate, a 95% confidence interval will be derived based on the Wilson's score method. Missing and invalid results (e.g. the results for one specific test for a given participant) will not be imputed and will be removed from the analysis.

Table 5 Definition of test results

	Reference Standard Outcome								
t		Reference positive	Reference negative	Total					
result	Test result Positive	ТР	FP	PP = TP + FP					
Test	Test result negative	FN	TN	PN = FN + TN					
	Total	P = TP + FN	N = FP + TN	P + N					

TP = true positives, TN = true negatives, FP = false positives, FN = false negatives, P = positive, N = negative

Analysis of the primary outcome(s)

Outcome 1.1

This outcome will be evaluated with the methodology described in section 4.1.1, using using blood culture as reference standard, on the PP population, for each test included in the trial. Outcome 1.2

This outcome does not require any statistical analysis.

Analysis of the secondary outcome(s)

Outcome 2.1

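### The stated precision of ±14 points with 80% power is not the precision of the planned interval: 100 samples give a 95% Wilson half-width of at most 9.6 points, and no test is planned

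*Combined protocol and SAP*

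**What the plan says.** All of the sample-size reasoning is in the Sample Size section. For planning, "sensitivity and specificity were both assumed to be 50" per cent, chosen as the worst case for precision. The target of at least 100 culture-positive and 100 culture-negative samples rests on that assumption and "on the feasibility of recruitment at the sites of enrolment, it was decided to set the sample size". The section then states the resulting precision, for sensitivity only: "with 80% power to detect a 95% confidence interval of width of +/- 14% in Kenya". It cites reference 11 and shows no formula. At 5% prevalence, 100 positives lead to an enrolment of at least 2,000.

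The analysis to which this should apply is set out elsewhere:

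- Primary Endpoint 1.1: "Point estimates of sensitivity and specificity for each test, with 95% confidence interval, using blood culture as reference standard".
- Description of statistical methods: "For each point estimate, a 95% confidence interval will be derived based on the" Wilson score method. Missing and invalid results "will not be imputed and will be removed from the analysis".
- Outcome 1.1 is analysed on the per-protocol set, defined as "all subjects in ITT for whom results for all tests are available".
- The detailed SAP "will be developed and finalized before the start of enrolment".

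**The concern.** A confidence interval width is not something a study has power to detect, so the sentence mixes two design calculations. If 14 is meant as the half-width of a 95% interval, it should agree with the planned Wilson method at 100 samples and 50%. If the 80% is meant as power, there should be a null value and a test.

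This is the only statement of expected precision in the documents. It would lead a reader to expect much wider intervals than the study will produce, and it implies a hypothesis test that the plan does not contain. It also gives nothing for specificity, which is half of the primary endpoint. Because a detailed SAP is to follow, the figure could be carried into it.

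**Working it through.** **Inputs.** n = 100 per group, p = 0.50, 95% confidence and 80% power (Sample Size); Wilson score interval (Description of statistical methods). Two-sided 5% is assumed, as the documents do not state sidedness; z = 1.960 and 0.842.

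**1. Reproducing the plan's figure.** The one-sample formula for a detectable difference d from a fixed proportion is d = (z₀.₉₇₅ + z₀.₈₀) × √(p(1−p)/n).

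- d = (1.960 + 0.842) × √(0.25/100) = 2.802 × 0.05 = 0.140.
- Inverted: n = 2.802² × 0.25 / 0.14² ≈ 100.

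So 14 points comes out almost exactly, but as the departure from 50% detectable with 80% power. That this is where it came from is an inference.

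**2. The planned interval at n = 100.** The Wilson half-width is z√(p̂(1−p̂)/n + z²/4n²) / (1 + z²/n). It is largest at p̂ = 0.5, where it reduces to 0.5z/√(n + z²).

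- 0.5 × 1.960 / √(100 + 3.84) = 0.980 / 10.19 = 0.096.
- Interval at 50/100: 40.4% to 59.6%. No other result out of 100 gives a wider one.
- Other methods do not reach 14: Wald 1.96 × √(0.25/100) = 9.8 points; exact (Clopper-Pearson) 39.8% to 60.2%, or 10.2 points.
- Ratio of stated to actual: 0.14 / 0.0962 = 1.46.

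**3. What n would ±14 points correspond to?**

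| Reading | Wilson n | Wald n |
|---|---|---|
| Half-width 14 points | 46 | 49 |
| Total width 14 points (half-width 7) | 193 | 196 |

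Neither reading gives 100. Nor can the 80% be the chance of achieving a half-width within 14 points: at n = 100 that chance is 100%, because no result exceeds 9.6.

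**4. Half-width at accuracies cited in the Sample Size section, n = 100.**

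| Observed value | Wilson half-width (points) |
|---|---|
| 50% | 9.6 |
| 69% | 8.9 |
| 78% | 8.0 |
| 87% | 6.6 |
| 90% | 6.0 |

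**5. Fewer evaluable samples.** The documents give no rate of loss, so these are illustrations. The maximum half-width 0.980/√(n + 3.84) is 10.1 points at n = 90, 10.7 at n = 80 and 11.4 at n = 70. Such numbers are possible before any result is removed: with exactly 2,000 enrolled and a true prevalence of exactly 5%, the 95% binomial range for the number of positives is 81 to 120, and the probability of at least 100 is 0.51.

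**6. Is there a target for the power?** Primary Endpoint 1.1 and the methods for Outcome 1.1 specify estimation only. No null value, performance threshold or significance test appears in the documents. The 50% is introduced as the worst case for sample size, not as a value to be tested against.

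**The case against.** The strongest defence is that the number was not miscalculated. From the plan's own inputs, 14 follows exactly as a detectable difference. The 80% can also be given a meaning in an estimation study, as the chance that the 95% interval excludes a value 14 points from the truth. With a true sensitivity of 50% and n = 100, the Wilson lower limit exceeds 36% with probability 0.82. On this view only the label is at fault. The figure is also attributed to reference 11, which was not available for this review, and the background does mention latent class modelling for an imperfect reference standard. Finally, the consequence is small: actual precision is better than stated, and no decision rule uses the 14.

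Much of this stands. The fault is a correct number attached to the wrong quantity, and it is conservative. But the sentence names a confidence interval width, and for that quantity 14 is wrong under any usual method at n = 100. The exclusion reading is not what the text says, and no objective concerns a 14-point difference. Whatever reference 11 contains, the Sample Size section gives no latent-class inputs and the planned analysis takes blood culture as the sole reference standard, so the figure does not describe that analysis.

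The range of 81 to 120 positives also depends on stopping at exactly 2,000. The plan says at least 2,000 and projects 2,520 presenting patients; if all of those were enrolled, which is not planned, the range would be 105 to 148. This affects only how likely a shortfall is, not the 9.6-point maximum at n = 100.

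**Conclusion.** The concern holds. As a description of the planned analysis, ±14 points overstates the worst-case half-width by a factor of 1.46; the correct maximum is 9.6 points, and 6.0 to 8.9 points at observed values from 90% down to 69%. The power statement has no stated hypothesis behind it.

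The 9.6 assumes 100 evaluable samples in the group and the Wilson method. With an assumed 80 to 90 evaluable the maximum is still only 10.1 to 10.7 points; it reaches 14 only at about 46 samples. The targets of 100 per group and 2,000 enrolled are unaffected, since the error is conservative and the number also rests on feasibility. It should be corrected because it is the plan's only precision claim for its primary endpoint.

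**What to change.** Replace the precision sentence in the Sample Size section with wording such as:

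> With 100 evaluable culture-positive and 100 evaluable culture-negative samples, the 95% Wilson interval for sensitivity or specificity has a half-width of at most 9.6 points (at 50%), about 8.0 points at 78% and 6.0 points at 90%. If missing or invalid results reduce the evaluable number in a group to 90 or 80, the maximum is 10.1 or 10.7 points.

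Delete the reference to 80% power. If a test against a fixed value is intended, state the null value, the difference, the sidedness and the test instead. If the 14 was obtained from reference 11, give the inputs and say that it does not describe the planned analysis against blood culture alone. Carry the corrected sentence into the detailed SAP.

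The cost is one sentence. Enrolment, endpoints and analysis stay as they are.

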Typhoid fever is an enteric bacterial infection caused by *Salmonella enterica* serovar Typhi (Salmonella Typhi; S. Typhi). It is an important infectious disease in low- and middle-income countries with over 10.9 million new cases worldwide and 116.8 thousand death in 2017. South Asia and Sub Saharan Africa are the most affected areas of the world. Typhoid fever is common in areas with inadequate sanitation and hyegine. In routine practice, diagnosis of typhoid fever is rarely confirmed as diagnostic tests are unavailable or have limited diagnostic accuracy. Blood culture is the commonest reference standard test but has a lower sensitivity. Alternatives to those methods exist but their performance is poor. The Widal test is still used but as it is based on cross-reactive antigens, it lacks sensitivity and specificity. Clinician often use rapid diagnostic tests to diagnose typhoid. A number of typhoid fever RDTs are commercially available but performance data are not available or not consistent from a study to another. This prospective, multicentre, cross-sectional study will be carried out in 3 hospitals of Nairobi, Kenya. 2000 clinically suspected typhoid cases will be enrolled in this study, blood culture as well as serum for RDT will be received. All typhoid positive and equal typhoid negative serum will be tested for investigational RDTs.

This collaborative study between KEMRI and FIND will systematically compare different point of care typhoid tests currently available in the market against the same set of reference standard. The knowledge gained from this trial may benefit health providers' by providing information on diagnostic accuracy of current typhoid test and to decide on utility of these commercial tests. The result obtained from this trial will also be made available to help inform Ministry of Health in Kenya and the WHO Essential Diagnostic list (EDL) and stakeholder decision making more broadly.

LAY SUMMARY

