All samples preparations (blood culture and serum preparation) will be conducted in parallel. Blood culture will be done using an automated blood culture system (BD BACTEC 9050). BACTEC vials will be processed as per manufacturer's instructions. Bottles will be incubated until signal-positive or till the end of day 5, whichever is earlier. When positive signal is observed, bottles are unloaded from instrument and Gram's stain and cultures and biochemical tests to identify *Salmonella* Typhi will be performed using standard microbiological procedures. Patients will be classified as typhoid or non-typhoid cases according to the blood culture results. However, since the results of the blood culture may take several days to be available, serum will be separated from all whole blood samples and will be aliquoted. It is expected that at least 100 blood culture positive and 100 blood culture negative samples will be tested with index tests and will be kept for long term storage.

Testing with the index tests will be performed in batch at the end of each month while the remaining volumes of the selected sera will be kept at -80°C. Depending on the initial volume that will differ between adult and children samples, 3 to 6 aliquots will be kept at -80°C for long term storage and will be used for future evaluation of diagnostic tests.

Investigational products

Reference standard tests to identify Salmonella Typhi:

All blood samples collected from study participants will undergo blood culture.

• Blood culture: Blood culture is considered as gold standard for the diagnosis of typhoid fever. Blood culture is a routine process for diagnosis of typhoid fever.

Index tests:

Index tests are RDTs that will be performed according to manufacturer's instructions by trained laboratory personnel. The readers of the index tests and reference standard test will be blinded to the results of the other tests.

Typhoid RDTs for inclusion in the study were selected by the study team based on a combination of the following criteria:

- RDT is CE-marked
- Published independent evaluation data
- International availability
- Volume of samples
- Price of the test
- Turnaround time

RDTs will be procured by FIND and shipped to the study sites in Kenya. There are no financial ties of any nature with the manufacutrers. All selected RDTs which will be included in the study are shown in Table 2.

Table: 2 Lists of RDTs

1	SD Bioline Salmonella Typhi IgG/IgM Fast

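### Enrolling 2,000 at 5% prevalence gives 100 culture-positives only on average, and the 2,520 used to show that 2,000 is reachable counts febrile presenters, not enrolled participants

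*Combined protocol and SAP*

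**What the plan says.** All of the sizing is in the combined protocol and SAP, mainly under Sample Size.

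- **Target.** "it was decided to set the sample size in order to recruit at least 100 culture positive and culture negative samples in Kenya". The precision attached to it is "80% power to detect a 95% confidence interval of width of +/- 14% in Kenya", with sensitivity and specificity both taken as 50%.
- **Enrolment.** "this number of positive samples requires the enrolment of at least 2,000 participants in Kenya (at a prevalence of 5"%). The 5% is a personal communication, given without a denominator or a range.
- **How firm the 2,000 is.** The opening summary says "2000 clinically suspected typhoid cases will be enrolled in this study". Study workflow repeats the yield: "It is expected that at least 100 blood culture positive and 100 blood culture negative samples will be tested with index tests".
- **Feasibility.** The starting figure is that "the average number of patients presenting with febrile illnesses at Mbagathi County Hospital was 20 per day"; the other two sites are put at 10 and 5 a day. "We plan to sample for only 3 days in a week (Mon-Wed) due to the observed trend of high patient inflow on these days". The total is 35 a day and 420 a month, and the section concludes: "This works out to a minimum of 2,520 which is above the sample size of 2,000 participants that we are targeting".
- **Who may enrol.** The Inclusion and Exclusion Criteria require age 8 to 65, at least three consecutive days of fever in the past seven, clinical suspicion of enteric fever, no known alternative cause, consent and enough blood.
- **Duration.** Project Time Frame gives approximately six months, and Table 7 shows six months of sample collection. The Budget Justification has the project supervisor coordinating sampling for nine months.

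**The concern.** The two figures answer two questions: will 2,000 participants supply the positives, and can the sites supply 2,000 participants? Neither answer is shown.

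First, dividing 100 by the prevalence gives the enrolment at which 100 is the expected count. The text presents it as the enrolment that secures at least 100, and no rule says what happens if fewer are found. The primary analysis uses the per-protocol set (results available for all tests), so missing results can only lower the number analysed.

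Second, the flow of 35 a day is built from patients presenting with febrile illness. It is compared directly with a number of participants who must pass several further criteria and consent. Calling it a minimum implies a margin of 520 that exists only if nearly four in five febrile presenters enrol.

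Culture-positives determine the precision of sensitivity, a primary endpoint, and they stock the biorepository, the other primary endpoint.

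**Working it through.** **Reproducing the plan's figures**

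- Positives: (1.96 + 0.842)² × 0.5 × 0.5 / 0.14² = 100.1. The plan does not print this formula; it is inferred because it returns the plan's 100 from 50%, 14 points, 95% and 80% power.
- Enrolment: 100 / 0.05 = 2,000.
- Flow: (20 + 10 + 5) × 3 days × 4 weeks = 420 a month; × 6 months = 2,520.

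All three reproduce.

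**(a) What 2,000 delivers**

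Take the number of positives as binomial with N = 2,000 and p = 0.05. The mean is 100, the SD is √(2,000 × 0.05 × 0.95) = 9.7, and the 2.5th and 97.5th percentiles are 81 and 120. P(at least 100) = 51.4%. Other prevalences are assumptions:

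| Prevalence | P(at least 100 positives in 2,000) |
|---|---|
| 4.5% | 15% |
| 5% | 51% |
| 5.5% | 85% |

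If 5% or 10% of positives were lost from the per-protocol set (assumed), P(at least 100 analysed) at 5% prevalence would be 31% or 15%.

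The precision lost is modest. At 50% sensitivity there are two scales. One is the expected half-width of the Wilson interval that the plan will report. The other is the margin that keeps 80% power, (1.96 + 0.842) × 0.5 / √n:

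| Positives | Wilson half-width | 80%-power margin |
|---|---|---|
| 100 | 9.6 points | 14.0 points |
| 90 | 10.1 | 14.8 |
| 80 | 10.7 | 15.7 |

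At the sensitivities cited in Sample Size, the 14-point margin needs fewer positives: about 86 at 69% and 69 at 78%.

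**(b) What 2,520 means**

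Fraction of febrile presenters that must enrol to reach 2,000:

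- six months of four weeks: 2,000 / 2,520 = 79%
- 26 weeks: 35 × 3 × 26 = 2,730; 2,000 / 2,730 = 73%
- nine months, as in the Budget Justification: 420 × 9 = 3,780; 2,000 / 3,780 = 53%

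The plan gives no enrolment fraction, so the fractions below are assumptions. The positives column also assumes that the 5% applies to enrolled suspected cases. Enrolled = 2,520 × f; positives = 0.05 × enrolled. Power for ±14 points at 50% sensitivity = Φ(0.14 × √n / 0.5 − 1.96).

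| Fraction f | Enrolled in six months | Expected positives n | Wilson half-width | Power for ±14 |
|---|---|---|---|---|
| 70% | 1,764 | 88 | 10.2 points | 75% |
| 60% | 1,512 | 76 | 11.0 | 68% |
| 50% | 1,260 | 63 | 12.0 | 60% |

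**The case against.** Several points on the other side carry weight.

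- **Dividing required cases by prevalence is common practice, and the text leaves room for more.** It says at least 2,000, and the workflow speaks of what is expected. That stands: the 51% applies only if enrolment stops at 2,000. But the summary and the Sample Size section both name 2,000 as the number to enrol. The budget heading for 2,400 samples and the 3,000 culture bottles suggest spare supply, yet no enrolment rule uses it.
- **The reported interval stays narrow.** This also stands. Even with 63 positives the expected Wilson half-width is 12.0 points. A reader might infer that the study will miss its ±14 points; the documents do not support that. What falls is the probability behind the stated 80%.
- **Positives need not fall in proportion to enrolment.** The plan does not say whether the 5% is among all febrile patients or among suspected cases. If all febrile, enrolling only suspected cases could raise the yield, and the fall would be smaller than in the last table.
- **The time limit is soft and the flow may be conservative.** Project Time Frame is approximate, the budget mentions nine months, and other weekdays are unused. The break-even is therefore a range from 53% to 79%, and a reader should not infer that 2,000 is unreachable. It has simply not been shown to be reachable in six months.
- **Per-protocol losses may be small.** The case report form provides for repeating invalid tests, which limits them. The 5% and 10% are illustrations only.

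**Conclusion.** The point holds as a matter of labels and unstated assumptions; the arithmetic itself is right. One hundred is the mean yield of 2,000 participants, with a 51% chance of being reached if enrolment stops there and prevalence is exactly 5%. On its own that has a modest effect.

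The 2,520 is a projection of patients available for screening, not a lower bound on participants. This half can matter more: six months requires 79% of presenters to enrol (73% counting 26 weeks), and the plan offers no evidence for such a fraction. At assumed fractions of 70% to 50%, with the 5% applying to those enrolled, positives would be about 88 to 63 and power for ±14 points about 75% to 60%. These power figures rest on the inferred formula and on 50% sensitivity, the plan's worst case.

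The plan should be corrected, but at the low end of that category: nothing here shows that the primary analysis would fail.

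**What to change.** 1. **Restate the yield.** Say that 2,000 participants are expected to give 100 culture-positives (95% range 81 to 120; 51% chance of at least 100 at 5% prevalence). Give the Wilson half-widths at 50% sensitivity for 100, 90 and 80 positives (9.6, 10.1 and 10.7 points), separately from the 80%-power margins (14.0, 14.8 and 15.7).
2. **Relabel the flow.** Call 2,520 the projected number of febrile presenters and delete the word minimum. Apply a stated eligibility-and-consent fraction, marked as an assumption with a range, and give the break-even: 79%, or 73% on 26 weeks, or 53% if sampling runs nine months. Reconcile the six months in Project Time Frame with the nine in the Budget Justification.
3. **Say which population the 5% describes**: all febrile patients or clinically suspected cases.
4. **Check early.** After the first month, replace the assumed fraction with the one observed in the screening log that Screen Failures and Trial Procedures already require.

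The cost is a few sentences and one tabulation of an existing log. The price in presentation is that the stated feasibility and assurance become less favourable.
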